## 8.0 Criteria for Response and Toxicity

(See Appendices C and E)

### 8.1 Tumor Measurements

- a. Lesions will be measured in centimeters prior to the course of therapy.
- b. The longest diameter and its perpendicular will be measured for bi-dimensionally measured lesion. Size will be reported as the product of the diameters.
- c. Measurements should be made and recorded by the physician.
- d. An estimate of overall objective and subjective response will be made and recorded at each visit.
- e. Endoscopy findings will be mapped out.

### 8.2 Response Definitions

- a) Clinical responses- The guidelines from the 'Report of an International Workshop to Standardized Response Criteria for Non-Hodgkin's Lymphoma' will be followed (35). (See Appendix E for Summary of Response Criteria for Non-Hodgkin's Lymphoma)

**CR** – 1) Complete disappearance of all detectable clinical and radiographic evidence of disease and disappearance of all disease-related symptoms if present before therapy, and normalization of the biochemical abnormalities (eg, lactate dehydrogenase [LDH] definitely assignable to lymphoma).

2) All lymph nodes and nodal masses must have regressed to normal size ( $\leq 1.5$  cm in their greatest transverse diameter for nodes  $>1.5$  cm before therapy.) Previously involved nodes that were 1.1 to 1.5 cm in their greatest transverse diameter before treatment must have decreased to  $\leq 1$  cm in their greatest transverse diameter after treatment, or by more than 75% in the sum of the products of the greatest diameters (SPD).

3) Any macroscopic nodules in any organs detectable on imaging techniques should no longer be present.

4) Flow cytometric, molecular, or cytogenetic studies are not considered part of routine assessment to document persistent disease at the present time.

**CR/unconfirmed (Cru)** – 1) Those patients who fulfill criteria 1 and 3 above, but with one or more of the following features: A residual lymph node mass greater than 1.5 cm in greatest transverse diameter that has regressed by more than 75% in the SPD. Individual nodes that were previously confluent must have regressed by more than 75% in their SPD compared with the size of the original mass.

**PR** – 1)  $\geq 50\%$  decrease in SPD of the six largest dominant nodes or nodal masses. These nodes or masses should be selected according to the following features: (a) they should be clearly measurable in at least two perpendicular dimension, (b) they should be from as disparate regions of the body as possible, and (c) they should be included mediastinal and retroperitoneal areas of disease whenever these sites are involved.

2) No increase in the size of the nodes, liver, or spleen.

3) No new sites of disease.

**Stable disease** is defined as less than a PR (see above) but is not progressive disease (see below).

**Relapsed disease** (CR, Cru) – 1) Appearance of any new lesion or increase by  $\geq 50\%$  in the size of previously involved sites.

2)  $\geq 50\%$  increase in greatest diameter of any previously identified node greater than 1 cm its short axis or in the SPD of more than one node.

**Progressive disease** (PR, nonresponders) – 1)  $\geq 50\%$  increase from nadir in the SPD of any previously identified abnormal node for PRs or nonresponders. 2) Appearance of any new lesion during or at the end of therapy.

b. Response Assessment

Response is assessed on the basis of clinical radiologic, and pathologic (i.e, bone marrow) criteria. CT scans remain the standard for evaluation of nodal disease. Thoracic, abdominal, and pelvic CT scans are recommended even if those areas were not initially involved because of the unpredictable pattern of recurrence.

A bone marrow aspirate and biopsy should only be performed to confirm a CR if it is clinically indicated by new abnormalities in the peripheral blood counts or blood smear.

c. Response durations are measured from the time of response (not the beginning of treatment) until there is evidence of progressive disease. Progression free survival will be measured from protocol entry.

8.3 Frequency of Response Determination: All lesions must be measured at baseline and then as per section 7.4

8.4 Survival Durations: The survival of patients will be measured from entry into protocol.

8.5 All toxicities encountered during the study will be evaluated according to the grading system (0-4) in Appendix C. Duration and treatment will be recorded. Life-threatening toxicities should be reported immediately to the study chairman who in turn must notify the IRB. Should this occur, it will mandate closure of the protocol to patient entry for investigation as to the reasons for this and a decision can be taken as to whether the protocol can remain open or should be closed.

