### 2.0 Background

2.1 Rationale- MALT lymphoma is a relatively recently described entity which is also known as extranodal marginal zone lymphoma (1)(2)(3)(4). It was initially recognized in gastrointestinal tract with the majority arising from the stomach. Nowadays, however, about 30 to 40% of the MALT lymphomas are thought to be of non-gastrointestinal origin according to the M.D. Anderson Cancer Center lymphoma data base and others (5). Though MALT lymphoma constitute about 7 to 8%(6) of non-Hodgkin's lymphoma, prospective clinical trials are scarce and optimal treatments still remain to be defined. It is generally considered to be a low grade lymphoma at early state (7)(8) having a very favorable prognosis even after localized treatments such as radiation therapy or surgical resection alone (9)(10). Most of the data on the treatments of MALT lymphoma come from experiences in gastric MALT lymphoma (11)(12)(13). There have been multiple retrospective series suggestive of favorable outcome for these patients. However, the first report on a prospective clinical trial in managing Ann Arbor stage 1 and 2 gastric MALT lymphoma with radiation therapy alone was published in 1998 and has been recently updated (14)(15). Twenty nine patients were treated with a median dose of 30 Gy (range 22.5 to 43.5) delivered at 1.5 Gy per fraction to the stomach and adjacent lymph nodes. At a median follow-up of 30 months, 94 % remain disease free. Non-gastric MALT lymphomas (16) (3)(5) have been reported in sites such as bowel (17) lung (18), breast (19)(20), skin (21), thyroid gland (22), bladder (23)(24), liver (25) dura (26)(27), esophagus (28) ocular adnexa (29)(30) along with other head and neck series limited by a small number of patients treated in a variety of different ways including any combination of chemotherapy, radiation therapy and surgery, thus yielding no significant insights into the optimal treatment except for the impression that most of them are very localized disease with favorable prognosis probably comparable to that of gastric MALT lymphoma (7). Therefore, we propose to prospectively study the efficacy and toxicity of radiation treatment for patients with stage 1 and 2 non-gastric MALT lymphoma as well as to verify the Memorial Sloan-Kettering Cancer Center data on gastric MALT lymphoma. Of note, a recent publication from the Non-Hodgkin's Lymphoma Classification Project reported an overall failure free survival of about 70% or higher if the International Prognostic Index is less than 4 in their retrospective analysis of 72 patients with stage 1 to 4 MALT lymphoma (33). Zinzani et al reported 5 year treatment failure rate of 70% for their review of 47 patients with stage 1 and 2 non-gastric MALT lymphoma(16). Based on the failure free survival curves presented in these studies, we believe it is a very reasonable hypothesis to test 75% or higher relapse free survival at 5 years with the majority of the relapses occurring within the first 5 years in our group of patients.

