### 4.0 Patient Eligibility

#### 4.1 Inclusion Criteria

- 4.1.1 Patients with newly diagnosed stage 1 and 2 MALT lymphoma are eligible for this study.
- 4.1.2 Patients with H. pylori positive gastric MALT lymphoma are recommended to have treatments with antibiotics prior to enrollment to this protocol.
- 4.1.3 Patients who failed other treatment modalities (e.g. chemotherapy, antibiotics therapy etc) are also eligible as far as they never had stage 3 or 4 disease during the course of the disease or disease progression to the opposite side of the diaphragm. (As the time course of the response to antibiotic therapy can be very variable among patients, sometimes requiring more than one year for complete response, failure to antibiotic therapy can be very variable among patients, sometimes requiring more than one year for complete response, failure to antibiotic treatment will be defined as no response or progression of the disease documented by endoscopy and biopsy.)
- 4.1.4 Patients who have had stage 4 diseases due to bilateral parotid gland or ocular/ocular adnexal involvement or due to multiple sites within Waldeyer's ring will still be eligible.

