6.1 A complete history and physical examination including performance status (Appendix B)

6.2 Laboratory studies will include a CBC with differential, platelet count, electrolytes, biochemical survey, TSH (if indicated due to the site of the disease), and beta-2 microglobulin. Imaging studies will include PA and lateral chest roentgenograms, CT of the neck, chest, abdomen, and pelvis. Esophogogastroduodenoscopy (EGD) needs to be done for every patient. If EGD is positive, colonoscopy along with small bowel series will be performed. Unilateral bone marrow biopsies will be obtained prior to initiation of therapy.

6.3 Location, type and size of all measurable lesions must be recorded prior to treatment.

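### The printed size rules for partial response and progressive disease count only lymph nodes, so extranodal primaries that shrink or regrow in place can be scored only as stable disease

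*Combined protocol and SAP*

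**What the plan says.** Section 2.1 introduces MALT lymphoma as "also known as extranodal marginal zone lymphoma". Section 8.2 then sets these response categories:

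- **CR** covers disease at any site. Criterion 1 is "Complete disappearance of all detectable clinical and radiographic evidence of disease", and criterion 3 adds organ nodules seen on imaging.
- **CRu** is for "Those patients who fulfill criteria 1 and 3 above" who also have a nodal residual, for example "A residual lymph node mass greater than 1.5 cm in greatest transverse diameter that has regressed by more than 75% in the SPD".
- **PR** needs at least a 50% "decrease in SPD of the six largest dominant nodes or nodal masses", with no growth of nodes, liver or spleen and no new site.
- **Stable disease** is whatever falls short of PR and is not PD.
- **PD**, for partial responders and non-responders, is growth of at least 50% from nadir in a known abnormal node, or a new lesion during or at the end of therapy.
- **Relapse** is a new lesion or growth of at least 50% at a previously involved site of any kind, but it is labelled for CR and CRu patients only.

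The measurements are not confined to nodes. Section 6.3 says "Location, type and size of all measurable lesions must be recorded prior to treatment". Section 8.1b says "The longest diameter and its perpendicular will be measured for bi-dimensionally measured lesion" and reports size as the product of the two. Section 8.1e has endoscopy findings mapped, and Section 8.3 has all lesions measured at baseline and on the follow-up schedule.

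On entry, Section 4.1.1 says "Patients with newly diagnosed stage 1 and 2 MALT lymphoma are eligible for this study". Neither 4.1 nor 4.2 requires disease to be present when radiation starts, and 8.2 has no category for a patient who is not evaluable for response.

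**The concern.** The typical lesion in this trial is an extranodal primary: stomach, orbit, lung, skin, salivary gland. The two categories that depend on change in size, PR and PD, are written for nodes, while the two that depend on presence or absence, CR and relapse, are written for any site. Section 8.2 is therefore inconsistent within itself, and measurements the plan already collects are not used by the rules that need them.

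Two things are at stake. Real shrinkage of a primary is reported as no response. Real regrowth of a primary that never cleared is not recorded as an event. Section 8.2c ends response duration at progressive disease and also defines progression-free survival (PFS), so both depend on the PD definition. Separately, without a rule for patients who start radiation with no assessable disease, the denominator of any reported response rate is undefined.

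**Working it through.** The plan gives no figure to reproduce on this point. The check applies the printed categories to one case: a single extranodal primary, no involved nodes, no new lesion. The inputs from the documents are the product of diameters (8.1b) and the 50% thresholds for PR and PD (8.2). The lesion sizes are illustrative assumptions.

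**Step 1: shrinkage.** Fall = 1 − follow-up product / baseline product, with a baseline of 5×5 = 25 cm².

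| Follow-up size | Fall in product | Category as printed | Category if PR covered all 8.1b lesions |
|---|---|---|---|
| 4×4 cm | 1 − 16/25 = 36% | Stable | Stable |
| 3×3 cm | 1 − 9/25 = 64% | Stable | PR |
| 2×2 cm | 1 − 4/25 = 84% | Stable | PR |
| 1×1 cm | 1 − 1/25 = 96% | Stable | PR |

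The third column follows by elimination. A visible lesion fails CR criterion 1, so CR is out. CRu needs the same criterion, so it is out too. PR needs a nodal sum of products, and there is none. No PD condition is met. Only stable disease remains.

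**Step 2: regrowth.** Increase = later product / nadir product − 1. From a nadir of 2×2 cm to 3×3 cm this is 9/4 − 1 = 125%, well above 50%. PD by size refers to a node, so it is not met. PD by new lesion is not met. Relapse requires an earlier CR or CRu, which this patient never had. The printed category is still stable disease.

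**Step 3: consequences.** With no PR, the patient in step 1 has no response and no response duration. With no PD, the regrowth in step 2 is not a progression event for PFS. If the size rules covered all lesions, the same patient would be a PR followed by PD.

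**Step 4: how many patients.** The documents do not say. The only response rate they give for radiation alone is in Section 2.2: 10 of 10 patients reached CR, so that series held no PR to misclassify. The exact two-sided 95% lower limit for 10 of 10 is 0.025^(1/10) = exp(−3.689/10) = 0.69. A share short of CR of up to 31% is therefore compatible with it. For the 35 planned non-gastric patients that is 0.31 × 35, or about 11, and only those among them without involved nodes would be affected as in steps 1 and 2. The series was supradiaphragmatic and six of the ten had conjunctival disease, so it cannot be carried over to the 40 planned gastric patients.

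**The case against.** The strongest reply is that 8.2 says the international workshop guidelines will be followed and points to Appendix E. Either source may hold rules for extranodal disease. Neither is in the text available here, and that absence is not a fault of the plan. The objection stands as a limit on certainty, but it does not remove the point. Section 8.2 prints definitions that staff will apply. If Appendix E differs, the two must be reconciled; if it matches, the gap is in both.

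A second reply is that 8.1d asks for an overall estimate of response at each visit and 8.1e maps endoscopy. Both are true, but neither is tied to a response category.

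A third is that little depends on response. Objective 1.1 speaks of efficacy without naming response, Section 11 is built on relapse-free survival (RFS), and ten of ten preliminary patients reached CR. This stands as a limit on the size of the problem.

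Three stronger readings are tempting, and the documents do not support them.

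- A reader might infer that CRu also counts only nodes. It does not: it requires CR criteria 1 and 3, which cover organs. Only the permitted residual is nodal, and refusing CRu to a patient with a visible organ lesion is coherent.
- A reader might infer that a patient whose lesion was excised before radiation scores as CR and inflates the CR rate. The text never says so. The word disappearance can be read to presuppose disease, in which case the patient has no category. The documents give no number of such patients. If a share r had no disease and the CR rate in the rest were c, the reported rate would be r + (1 − r)c; with c = 1, as in Section 2.2, this is 1 for every r, so there is no inflation.
- A reader might infer that the RFS design figures are wrong as a result. No accrual goal, precision or stopping-rule figure uses a response rate, and the relapse definition covers any previously involved site.

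**Conclusion.** The point holds for the printed PR and PD size criteria. A node-free extranodal primary that shrinks by 50% or more but stays visible is scored as stable disease. One that never clears and then regrows by 50% or more in place, without a new lesion, meets neither the PD nor the relapse definition.

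The effect is confined to response categories, response duration and PFS. It is total for a patient of this kind, but the number of such patients is unknown and may be small. The conclusion rests on reading 8.2 as operative and on Appendix E not overriding it.

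On patients without disease at the start of radiation, the supported statement is narrower: the plan has no rule for them, so the response denominator is open. This should be corrected, because the rule as stated misclassifies and the data needed to correct it are already collected.

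**What to change.** In Section 8.2:

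1. Apply the PR rule (decrease of at least 50%) and the PD size rule (increase of at least 50% from nadir) to the sum of products of all lesions measured under 8.1b, nodal and extranodal.
2. State how endoscopic findings mapped under 8.1e count towards each category, since much gastric disease may not be measurable in two diameters.
3. Leave CRu unchanged. Extending it to organ lesions would contradict its own requirement of CR criteria 1 and 3.
4. Reconcile the wording with Appendix E, and state any departure from the workshop criteria.

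In Section 11, add one line. Patients with no disease at the start of radiation, whether measurable or assessable by endoscopy or other means, are reported as not evaluable for response but are included in RFS, with a sensitivity analysis of RFS excluding them. The evaluable set should not be limited to lesions recorded under 6.3: that section covers measurable lesions only and would drop patients whose disease is seen only at endoscopy.

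The cost is wording. No patients, visits or measurements are added. The drawbacks are a slightly smaller denominator for response and a stated departure from the nodal-only text.

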## 9.0 Criteria for Removal from the Study

9.1 Progressive disease during radiation therapy which encompasses all known tumors.

9.2 The development of unacceptable toxicity defined as unpredictable, irreversible, or Grade 4.

9.3 Non-compliance by patient with protocol requirements.

9.4 Patient refusal.

## 10.0 Data and Protocol Management

10.1 Protocol Compliance: The attending physician must see each patient prior to the start of irradiation and at each follow-up visit post-treatment. All required interim and pretreatment data should be available and the physician must make a designation as to tumor response and toxicity grade.

10.2 Data Entry: Data must be entered into the Protocol Data Management system before therapy can be given. A brief explanation for required but missing data should be recorded as a comment.

10.3 Accuracy of Data Collection: The study chairman will be the final arbiter of response or toxicity should be a difference of opinion exist.

## 11.0 Statistical Considerations and Stopping Rules

This is a trial to estimate the relapse-free survival rate (RFS) of patients with gastric and non-gastric MALT lymphoma treated with radiation therapy alone. Patient accrual is expected to be 10 – 15 per year for gastric and 5 – 10 per year for non-gastric MALT lymphoma at initial presentation. Accrual of less than 5 patients per year for either gastric or non-gastric MALT lymphoma is expected for presentation upon failure of other treatment modalities. The patient accrual and outcome analyses will be done separately in the following 4 groups: Gastric vs non-gastric MALT at initial presentation vs upon failure to other treatment(s).

#### Accrual goals

The accrual goals for the patients at initial presentation are 40 for gastric and 35 for non-gastric MALT lymphoma. Based on the expectation that the relapse rate after radiation therapy alone will be 25% and that 70% of the relapsing patients will fail within 5 years, these numbers will provide a 95% confidence bound of +/- 5.9% for estimating the 2-year RFS. This calculation assumes that RFS follows an exponential distribution and we will follow all patients for at least 2 years.

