#### Stopping Rules for patient accrual at initial presentation

Based on the expectation that the relapse rate after radiation therapy alone will be 25% or less, RFS will be evaluated in each of the two subgroups of previously untreated patients and accrual stopped in RFS is < 70% after the first 15, 30, or 45 patients have been followed for a minimum of 2-years. Assuming that 70% of the relapsing patients will fail within 5 years, computer simulations indicate that this stopping rule will terminate patient accrual in both the gastric and non-gastric arms of the trial with a probability of 1% if the relapse rate is 25% with a 17% probability if the relapse rate is 50%, and with a probability of 60% if the relapse rate is 75%.

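### The single ±5.9% precision for 2-year RFS fits all 75 patients combined; the separately analysed groups get about ±8.1% (40 gastric) and ±8.7% (35 non-gastric)

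*Combined protocol and SAP*

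**What the plan says.** Section 11.0, Accrual goals, states: "The accrual goals for the patients at initial presentation are 40 for gastric and 35 for non-gastric MALT lymphoma". The planning assumption is that "the relapse rate after radiation therapy alone will be 25% and that 70% of the relapsing patients will fail within 5 years", and the conclusion drawn is that "these numbers will provide a 95% confidence bound of +/- 5.9% for estimating the 2-year RFS". On method, the paragraph adds only this: "This calculation assumes that RFS follows an exponential distribution and we will follow all patients for at least 2 years".

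On the unit of analysis, the opening paragraph of Section 11.0 states: "The patient accrual and outcome analyses will be done separately in the following 4 groups". The stopping rule for patients at initial presentation follows the same line: "RFS will be evaluated in each of the two subgroups of previously untreated patients". No RFS analysis of the gastric and non-gastric patients combined is described.

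**The concern.** One symmetric bound is given beside two different group sizes. Under one formula and the same follow-up, 40 and 35 patients cannot have the same precision, so the figure must refer to something the paragraph leaves out: a combined total, or an estimator whose information differs by group.

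This matters because the bound is the only stated basis for the goals of 40 and 35, in a trial whose declared purpose is to estimate RFS. Since the analyses are by group, a reader is likely to take ±5.9% as the precision each group's result will have. If it is really the combined figure, the estimates that the plan does intend to make have no stated precision, and the one that is stated belongs to an estimate it does not describe making.

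**Working it through.** **Inputs, all from Section 11.0, Accrual goals:** relapse rate 25%; 70% of relapses within 5 years; exponential RFS; every patient followed at least 2 years; n = 40 and 35, total 75.

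**2-year RFS**

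- Relapsed by 5 years: 0.25 × 0.70 = 0.175, so 5-year RFS = 0.825.
- Hazard: λ = −ln(0.825)/5 = 0.03847 per year.
- 2-year RFS: S = exp(−2λ) = 0.9259.

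**Reproducing the stated figure.** With no censoring before 2 years, the Kaplan-Meier estimate at 2 years is a simple proportion, with 95% half-width 1.96 × √(S(1 − S)/n). For n = 75 this is 1.96 × √(0.9259 × 0.0741/75) = 5.93%, which rounds to the stated 5.9%. Solving the other way, n = 1.96² × 0.9259 × 0.0741/0.059² = 75.7.

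**The same calculation by group.** The second estimator is an exponential fit with follow-up cut at 2 years (delta method), with half-width 1.96 × 2 × S × λ/√(n(1 − S)).

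| n | Proportion or Kaplan-Meier | Exponential fit cut at 2 years |
|---|---|---|
| 75 (combined) | 5.93% | 5.93% |
| 40 (gastric) | 8.12% | 8.11% |
| 35 (non-gastric) | 8.68% | 8.67% |

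The ratios to the combined figure are 8.12/5.93 = 1.37 and 8.68/5.93 = 1.46. The exponential assumption alone does not bring either group to 5.9%.

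**Other readings of the inputs**

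- A one-sided bound (1.645 in place of 1.96) gives 6.81% for 40 and 7.28% for 35.
- If 25% of patients relapse and the exponential applies only to their relapse times, 2-year RFS is 90.4%, and the half-widths are 9.11% for 40 and 9.74% for 35.

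All four per-group values are above 5.9%.

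**Using follow-up beyond 2 years.** Suppose accrual is uniform over A = n/rate years and follow-up continues until 2 years after the last entry. The expected number of relapses is d = n × [1 − (exp(−2λ) − exp(−(2 + A)λ))/(Aλ)], and the half-width of the exponential estimate is 1.96 × 2 × S × λ/√d. With the accrual rates from the opening of Section 11.0:

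| Group | Rate per year | Half-width |
|---|---|---|
| Gastric, n = 40 | 10 / 12.5 / 15 | 5.86% / 6.15% / 6.37% |
| Non-gastric, n = 35 | 5 / 7 / 7.5 / 10 | 5.44% / 5.94% / 6.05% / 6.46% |

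**Shape of the interval.** Expected relapses by 2 years are 40 × 0.0741 = 2.96 and 35 × 0.0741 = 2.59. With so few, a symmetric bound describes the interval poorly: 92.6 + 8.1 = 100.7% and 92.6 + 8.7 = 101.3%. Averaged over the binomial distribution of outcomes, the exact (Clopper-Pearson) 95% interval reaches 12.6 points below and 5.5 above the estimate for 40 patients, and 13.8 below and 5.7 above for 35.

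**The case against.** The strongest objection is that no arithmetic error has been shown. On the combined reading ±5.9% is correct, and the defect is a missing label. On a per-group reading it may also be correct. The paragraph assumes an exponential distribution and at least 2 years of follow-up, so patients who enter early are followed for longer, and an exponential fit would use that time. At 10 gastric patients per year the half-width is 5.86%, and at 7 non-gastric patients per year it is 5.94%; both round to 5.9%. The plan states "Patient accrual is expected to be 10 – 15 per year for gastric and 5 – 10 per year for non-gastric MALT lymphoma at initial presentation", so both rates are within range, and nothing ties one group's rate to the other's. Slower non-gastric accrual would also explain why unequal groups share one figure.

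This stands as a possibility, and it is why the combined reading is called an inference. It is the weaker explanation. It needs a particular pair of rates, whereas the match at 75 needs nothing beyond the paragraph's own inputs. Taking both groups at the low, middle or high end of their ranges does not give 5.9% for both. The paragraph cites no accrual rate and does not mention using later follow-up. If that method was meant, a reader cannot recover it, so the text needs correcting on either reading.

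Two further points are fair. Symmetric bounds that pass 100% are a poor replacement unless an exact or log-log interval goes with them. The practical consequence is also limited: each group's reported interval will rest on its own data, whatever was projected.

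**Conclusion.** The concern holds. At 2 years, on the plan's own inputs, the precision is about ±8.1% for the 40 gastric patients and ±8.7% for the 35 non-gastric patients, against the stated ±5.9%, which is reproduced at n = 75. A per-group ±5.9% at 2 years would need about 76 patients in each group.

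These values assume exponential RFS with 82.5% relapse-free at 5 years, no loss to follow-up before 2 years, and an estimate that does not use later follow-up. If later follow-up is used through an exponential fit, the per-group range is 5.9–6.4% for 40 patients and 5.4–6.5% for 35 over the plan's accrual rates.

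This should be fixed, because the figure is the sole stated rationale for the sample size. It does not affect trial conduct: the stopping rule uses the RFS estimate and not the width of its interval.

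**What to change.** In Section 11.0, Accrual goals:

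1. State the precision for each group, about ±8.1% for 40 gastric and ±8.7% for 35 non-gastric patients, and name the estimator.
2. Label ±5.9% as the figure for all 75 patients combined, or delete it.
3. If ±5.9% was meant for each group from an exponential fit to all follow-up, say so and give the accrual rate assumed for each group.
4. State that each group's 2-year RFS will be reported with an exact or log-log Kaplan-Meier 95% interval, and illustrate it. With 3 relapses, the exact interval is 79.6–98.4% for 37/40 and 76.9–98.2% for 32/35. This shows the asymmetry that a ± figure hides.

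The cost is wording only. The stated precision becomes less favourable, and no extra patients are needed.

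### The ±5.9% precision for 2-year RFS matches the two groups pooled; for each group analysed separately it is about ±8 to ±10%, and the stopping probabilities appear to rest on a different relapse model

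*Combined protocol and SAP*

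**What the plan says.** Section 11.0 describes a trial to estimate RFS and states that "The patient accrual and outcome analyses will be done separately in the following 4 groups": gastric or non-gastric, at initial presentation or after failure of other treatment.

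Under Accrual goals, "The accrual goals for the patients at initial presentation are 40 for gastric and 35 for non-gastric MALT lymphoma". The planning premise is that "the relapse rate after radiation therapy alone will be 25% and that 70% of the relapsing patients will fail within 5 years". On that basis "these numbers will provide a 95% confidence bound of +/- 5.9% for estimating the 2-year RFS". Two conditions are attached: "This calculation assumes that RFS follows an exponential distribution", and "we will follow all patients for at least 2 years". The plan does not say whether the bound is for each group or for both together, or how it was computed.

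The next paragraph, on stopping rules at initial presentation, evaluates each subgroup after 15, 30 and 45 patients have at least 2 years of follow-up, and stops accrual if RFS is below 70%. It repeats the assumption that 70% of relapses fall within 5 years and reports that "computer simulations indicate that this stopping rule will terminate patient accrual" with probability 1%, 17% or 60% when the relapse rate is 25%, 50% or 75%. It names no distribution.

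**The concern.** One bound is quoted for two groups of different size that are to be analysed apart. It is also tied to a single exponential, which has no plateau, while the premise in the same paragraph is that only a quarter of patients relapse. If the bound is a pooled figure, it describes an analysis the plan does not intend. If the stopping probabilities come from another relapse model, the two paragraphs of Section 11 describe different patient populations. The ±5.9% is the only quantitative support given for the goals of 40 and 35, so a reader would expect each group's estimate to be much tighter than it will be.

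**Working it through.** **Inputs.** All are from Section 11.0: 40 and 35 patients (75 together); 25% relapse, 70% of it by 5 years; at least 2 years of follow-up for everyone, so no administrative censoring before 2 years; stop if RFS is below 70% at 15, 30 or 45 patients.

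**Step 1: reproduce ±5.9%.** Relapse by 5 years is 0.25 × 0.70 = 0.175, so 5-year RFS is 0.825. One exponential through that point gives 2-year RFS = 0.825^(2/5) = 0.926. The half-width is 1.96 × √[S(1 − S)/n]:

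- n = 75: 1.96 × √(0.926 × 0.074/75) = 5.93 points, the plan's figure
- n = 40: 8.1 points
- n = 35: 8.7 points

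**Step 2: compare the exponential with its own premise.** The hazard is −ln(0.825)/5 = 0.0385 per year. The curve passes 75% at −ln(0.75)/0.0385 ≈ 7.5 years and keeps falling, so it cannot represent a population in which 25% ever relapse.

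**Step 3: find which model fits the stopping probabilities.** Let r be the relapse rate.

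- Single exponential: 2-year RFS = (1 − 0.7r)^0.4, which is 0.926, 0.842 and 0.742 for r = 25%, 50% and 75%.
- Mixture (a share r relapses, with exponential times and 70% of relapses by 5 years; the rest never relapse): 2-year RFS = 1 − r(1 − 0.3^0.4) = 1 − 0.382r, which is 0.904, 0.809 and 0.713.

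For one arm, RFS below 70% means at most 10 of 15, 20 of 30 or 31 of 45 patients relapse-free at 2 years. Exact sequential binomial probabilities of having stopped are:

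| Relapse rate | Plan | Mixture, looks at 15/30/45 | Exponential, looks at 15/30/45 | Mixture, looks at 15/30 only |
|---|---|---|---|---|
| 25% | 1% | 1.07% | 0.36% | 1.06% |
| 50% | 17% | 16.5% | 8.1% | 15.5% |
| 75% | 60% | 59.2% | 44.6% | 51.7% |

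With three looks the mixture is within 1 point of all three stated values. The exponential misses by about 9 points at 50% and 15 points at 75%.

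**Step 4: precision under the mixture.** The base case is 2-year RFS = 1 − 0.25 × 0.382 = 0.904. Half-widths are 6.65 points (n = 75), 9.1 (n = 40) and 9.7 (n = 35).

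**Step 5: split the widening.** The model change alone is 6.65/5.93 = 1.12. Using each group's own n multiplies the half-width by √(75/40) = 1.37 or √(75/35) = 1.46. Together these give about 1.5 (gastric) and 1.6 (non-gastric).

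**The case against.** The strongest reply is that ±5.9% need not be a pooled figure. A parametric exponential fit in each group gains from follow-up beyond 2 years. With uniform accrual plus 2 years, the half-width is 1.96 × 2Sλ/√(expected events). For 40 gastric patients at 10 per year, follow-up runs from 2 to 6 years, about 5.7 events are expected, and the half-width is 1.96 × 2 × 0.926 × 0.0385/√5.7 ≈ 5.9 points. Across the plan's accrual rates the result is about 5.4 to 6.5 points. This stands as a possible origin, and the documents do not settle it. It does not rescue the figure: the gain comes entirely from the exponential shape, which conflicts with the premise that only 25% of patients relapse.

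A second reply is that an exponential is a common approximation over a short horizon, and that the two models differ by only 2.1 points at 2 years (92.6% against 90.4%). That is fair. The model mismatch alone would be a small matter; per-group sample size drives most of the change.

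A third is that the mixture is inferred. This also stands. The match needs per-arm stopping and a look at 45 patients. The text speaks of stopping in both arms, and joint stopping under the mixture would be about 0.01%, 2.7% and 35%. The 45-patient look lies beyond both accrual goals. The nearest single-exponential variant tried (either arm stops, looks at 15 and 30) gives 0.7%, 15.2% and 63.3%, which fits less well.

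Two stronger readings are tempting. A reader might infer that 82.5% at 5 years contradicts Section 2.1, but the hypothesis there is "75% or higher relapse free survival at 5 years", and 82.5% satisfies it. A reader might also infer that the final analysis will fit an exponential and so be biased. The exponential statement describes the planning calculation, and no section specifies such an analysis.

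**Conclusion.** The point holds in this form. ±5.9% is reproduced by pooling 75 patients under a single exponential, and does not describe the precision of a 2-year proportion in either group that the plan analyses. Those half-widths are ±8.1% and ±8.7% under the same exponential, and ±9.1% and ±9.7% under the mixture that best matches the stopping probabilities. The single exponential does not reproduce 1%, 17% and 60% under the three-look, per-arm rule, so the two paragraphs appear to use different models.

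This rests on complete 2-year follow-up, the normal approximation that recovers the plan's own number, and, for the last pair of half-widths, the inferred mixture. At these sizes the symmetric form is itself rough (92.6 + 8.1 exceeds 100%), so the figures are planning magnitudes. The finding does not show that the accrual goals are wrong, only that the precision attached to them is too favourable.

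**What to change.** Use one relapse model for both the accrual-goal and stopping-rule paragraphs of Section 11, name it, and state the 2- and 5-year RFS it implies. Then replace ±5.9% with per-group precision:

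- **If the mixture is adopted:** 2-year RFS 90.4%, 5-year RFS 82.5%, about ±9.1% for 40 gastric and ±9.7% for 35 non-gastric patients. The stated stopping probabilities can remain if the sponsor confirms that they were simulated this way, per arm and with all three looks.
- **If the exponential is kept:** 2-year RFS 92.6%, 5-year RFS 82.5%, about ±8.1% and ±8.7%. The stopping probabilities must then be restated, and the 25% relapse premise reworded, because an exponential has no such ceiling.

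The cost is a change of text and a less favourable stated precision. Enrolment is unchanged.
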